10.2.11 Urine drug screen

Urine will be screened for drugs of abuse at screening using the AlereTM Drug Screen Test Panel. Additional random tests can be performed during the study period.

10.2.12 Alcohol breath test

An alcohol breath test will be performed at screening. Additional random tests can be performed during the study period.

10.2.13 Carbon monoxide measurement

Measurement of carbon monoxide (CO) in exhaled air will be performed at visits to the clinic.

10.3 Assessments related to primary endpoints

10.3.1 Pharmacokinetic samples and analysis

Venous blood samples (approximately 5 mL) for the determination of plasma concentrations of nicotine after administration of the IP, will be collected through an indwelling venous catheter at the pre-specified time-points (see Table 8.1-1 in Section 8.1). The following time windows will apply for the PK sampling:

- \pm 1 minute for time-points up to 30 minutes post-dose.
- \pm 2 minutes for time-points up to 90 minutes post-dose.
- \pm 5 minutes for time-points up to 6 hours post-dose.

The date and time of collection of each sample will be recorded in the CRF.

The blood samples will be collected in pre-labelled tubes. All the collected blood samples will be centrifuged to separate plasma. The separated plasma from each blood sample will be divided into 2 aliquots in pre-labelled cryotubes and frozen at -20°C.

For further details see lab manual.

Plasma samples for determination of plasma concentrations of nicotine will be analysed by ABS Laboratories Ltd by means of a validated using LC-MS/MS method. Samples from all evaluable subjects will be analysed.

10.4 Assessments related to secondary endpoints

10.4.1 Samples for analysis of Methyl salicylate

Plasma samples for determination of plasma concentrations of nicotine will also be analysed for plasma levels of salicylic acid which is a proxy for plasma levels of the flavour component Methyl salicylate. The levels of salicylic acid will be used for read-across to assess the plasma levels of Methyl salicylate.

The analysis of salicylic acid will only be performed for samples drawn during the experimental session when the IP is containing the flavour component i.e. ZYN® Wintergreen 6 mg and Longhorn Wintergreen pouch.

Plasma samples for determination of plasma concentrations of salicylic acid will be analysed by ABS Laboratories Ltd by means of a validated using LC-MS/MS method. Samples from all evaluable subjects excluding withdrawn or dropout subjects will be analysed.

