HIV, Hepatitis B and C	x		
Pregnancy test ³	X		
Drugs of abuse	X	x ⁴	
Alcohol screen	x	x ⁴	
CO measurement	X	x	
Randomisation		x ⁵	
IP (pouch) administration		x	
PK blood sampling		x ⁶	
Collection of pouches		х	
Treatment-emergent AEs (TEAEs)8		x	x
Baseline events	X	x ⁷	
Prior and concomitant medications ⁹	X	x	X

¹ Visit 1 could be performed during 2 days

² Refer to section 8.1.3, Schedule of Events per visit for, details.

³ Female subjects only

⁴ Drug and alcohol tests during the treatment period may be performed randomly.

⁵ Only on visit 2

⁶ Before and 5, 10, 15, 30, 60, 90, 120, 240 and 360 min after application of the investigational products

⁷Only prior to dose administration at Visit 2.

⁸ From first administration of IP.

⁹ For definitions of prior and concomitant medication, see Section 10.2.7.

Table 8.1-2 Detailed schedule of events for each treatment period

Visit					V	Visit 2 to 8	∞					
Assessment/time-point	Admission	Pre- dose	•	min 5	10	15 min	min	min	min	2 h	4 h	6
Inclusion/exclusion criteria	x ¹											
CO measurement	×											
Drugs of abuse	x ²											
Randomisation		X ³										
IP (pouch) administration			×									
IP (pouch) collection								X ⁴				
PK blood sampling		×		×	×	×	×	×	×	×	×	
Treatment-emergent AEs (TEAEs)							×					
Prior and concomitant medications						×						

¹ Confirmation of inclusion/exclusion criteria (Visit 2 only).

MW001TEMP01_02CSP

² Drug tests during the treatment period may be performed randomly
³ Only on visit 2

⁴ Collection of pouch +/- 1 (one) minute from specified time.

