8.8.1 General restrictions

- Subjects shall abstain from snus and all other nicotine containing products from 8.00 p.m. the night before each study day.
- Subjects shall abstain from smoking the last 24 hours before each study day.
- The subjects are not allowed to eat or drink or use any other mouth related procedure (e.g. tooth brushing) 30 minutes before dose administration, during application of investigational products and 30 minutes after the investigational product have been taken out. ³.
- The female volunteers are expected to be sexually abstinent or use non-systemic contraceptives to prevent pregnancy during the study period.

- Abstain from use of Methyl salicylate containing products, e.g. ointments, mouth wash and chewing gum.
- Abstain from drugs of abuse from Screening to the Follow-up visit.
- The subjects must not donate blood or plasma during the study until three months after the Follow-up Visit.
- Study subjects are not allowed to participate in any other clinical study during the study period i.e screening to follow up.

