8.8.2 Prior and concomitant therapy

Female systemic contraceptives e.g. birth control pills, injectable steroids, vaginal ring, transdermal patch and contraceptive implants are not allowed in the study.

Other concomitant medications or therapies, including herbal remedies, vitamin supplements and over-the-counter (OTC) products, will be allowed during participation in the study.

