16.6.4 Analysis of plasma levels of Methyl salicylate

Plasma levels of Methyl salicylate will be summarized using descriptive statistics.

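### Methyl salicylate uptake is read from plasma salicylic acid, but the restrictions cover only methyl salicylate products and leave other sources of the measured analyte permitted

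*Protocol*

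**What the plan says.** **Analyte.** Secondary objective 5 (Protocol section 7.2) asks for plasma levels of methyl salicylate after the wintergreen pouches. Section 10.4.1 plans no assay of that compound. Plasma is "analysed for plasma levels of salicylic acid which is a proxy for plasma levels of the flavour component Methyl salicylate", and "The levels of salicylic acid will be used for read-across to assess the plasma levels of Methyl salicylate".

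**Sessions assayed.** Section 10.4.1 also says "The analysis of salicylic acid will only be performed for samples drawn during the experimental session when the IP is containing the flavour component". That means ZYN Wintergreen and Longhorn Wintergreen, two of the seven sessions.

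**Restrictions.** The only salicylate restriction is in section 8.8.1: "Abstain from use of Methyl salicylate containing products, e.g. ointments, mouth wash and chewing gum". Section 8.8.2 rules out systemic contraceptives for women and then states "Other concomitant medications or therapies, including herbal remedies, vitamin supplements and over-the-counter (OTC) products, will be allowed during participation in the study".

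**Analysis.** Section 16.6.4 is one sentence: "Plasma levels of Methyl salicylate will be summarized using descriptive statistics".

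**Data already collected.** The sampling times in Table 8.1-1 are "Before and 5, 10, 15, 30, 60, 90, 120, 240 and 360 min after application of the investigational products", so each assayed session has its own pre-dose sample. Section 10.2.7 requires concomitant medication to be recorded with name, total daily dose and start and stop dates.

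**The concern.** The restriction in section 8.8.1 shows that the sponsor saw outside exposure as a threat to this endpoint. The control it wrote names the flavour compound, whereas the laboratory measures salicylic acid. Acetylsalicylic acid and other salicylate medicines also give rise to salicylic acid. This is general pharmacology, which the protocol does not state, and it is taken here as an assumption. Section 8.8.2 leaves those medicines open to subjects.

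Objective 5 depends on attributing the measured salicylic acid to the pouch. If some of it comes from elsewhere, a table headed methyl salicylate would include exposure that the product did not cause. The rules on what subjects may take and which sessions are assayed are conduct rules in the protocol, so a later statistical analysis plan cannot repair that part.

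**Working it through.** The protocol states no figure for this endpoint, so there is none to reproduce. The main check sets the sections against each other.

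1. **What is measured:** salicylic acid (10.4.1).
2. **What is restricted:** products containing methyl salicylate (8.8.1).
3. **What is permitted:** everything else apart from systemic contraceptives for women (8.8.2). Any source of salicylic acid that is not a methyl salicylate product falls here.
4. **Would the analysis set remove an affected subject?** Section 16.3.2 excludes subjects for major protocol deviations. Taking a permitted medicine is not a deviation, so the subject stays in.
5. **Is there a control session?** The five sessions without wintergreen are not assayed for salicylic acid. The only internal reference is the pre-dose sample of the same session.
6. **Would the medication record identify the session?** In part. Section 10.2.7 asks for dates and not clock times, so a tablet on the day of a visit may not be placed before, during or after sampling. The pre-dose sample reveals intake before the session, not intake during the six hours.
7. **Does any section connect steps 5 and 6 to the analysis?** None does. Section 16.6.4 names neither the pre-dose level nor the medication record.

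**Illustration on assumed values.** Neither the frequency of affected sessions nor their level is in the document.

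*Chance of at least one affected session.* With 32 evaluable subjects (synopsis) and two wintergreen products there are 32 × 2 = 64 sessions. If each is affected independently with probability p, the chance is 1 − (1 − p)^64:

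| Assumed p | Chance of at least one |
|---|---|
| 1% | 47% |
| 2% | 73% |
| 5% | 96% |

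*Effect on one product's arithmetic mean.* If 31 subjects have level m and one has k × m, the mean is (31m + km)/32 = m × [1 + (k − 1)/32]:

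| Assumed k | Mean multiplied by |
|---|---|
| 5 | 1.13 |
| 10 | 1.28 |
| 50 | 2.53 |
| 100 | 4.09 |

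The SD and maximum would rise as well. The median of 32 values shifts by at most one rank when a single value is raised, so it would barely move.

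**The case against.** Four arguments have weight on the other side.

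**Baseline handling belongs in the statistical analysis plan.** Section 16 says that a more detailed plan will follow. A reader might infer from section 16.6.4 that unadjusted levels will be summarised whatever the data show. The document does not say so; the sentence is silent, and the unseen plan may add a pre-dose correction or an exclusion rule. This stands, and the absence of such rules is not the point made here. The mismatch between restriction and analyte remains, because it is fixed in sections 8.8.1, 8.8.2 and 10.4.1.

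**An affected session could be noticed.** Section 16.1 provides medians, summaries by assessment time where applicable, and individual listings. A raised background would show at the pre-dose time point. This also stands. A reader might infer that a salicylate tablet would inevitably be taken for flavour uptake; the document supports only that it could be.

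**The size is unknown.** A tempting calculation compares a 500 mg acetylsalicylic acid tablet (500 × 138.12/180.16 = 383 mg salicylic acid) with a pouch assumed to hold 1 to 3% methyl salicylate. Multiplying by 138.12/152.15 gives 3.6 mg for a 0.4 g ZYN pouch at 1%, up to 40.9 mg for a 1.5 g Longhorn pouch at 3%, so the tablet holds roughly 9 to 106 times more. Only the pouch weights are in the protocol. The ratio compares whole masses, not plasma levels over six hours, and ignores when the tablet was taken. It does not support a claim about the size of the distortion.

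**A narrow restriction beside a general permission is not a formal contradiction.** True: a subject can obey both sections. The difficulty is that obeying both does not protect the endpoint the restriction appears meant to protect.

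**Conclusion.** The point holds as a mismatch between sections 8.8.1, 8.8.2 and 10.4.1. Sources of the measured analyte other than methyl salicylate products are permitted, their use is not a deviation, and as written an affected wintergreen session remains in a summary labelled methyl salicylate. Such a session could distort the mean, SD and maximum, and the median much less.

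The size cannot be estimated from the document, which gives no methyl salicylate load, no expected plasma level and no frequency of salicylate use. The figures above are illustrations on assumed values. The conclusion rests on one outside assumption, that common salicylate medicines raise plasma salicylic acid.

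The reach is limited to descriptive secondary objective 5. The primary nicotine AUCinf comparison, the sample size and the nicotine-based wintergreen comparison (objective 2) are not affected.

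**What to change.** 1. **Sections 8.8.1 and 8.8.2:** reconcile them with the analyte named in section 10.4.1. Which products to restrict, if any, is for the sponsor to decide.
2. **Section 16.6.4, label:** report the result as salicylic acid, and keep the read-across to methyl salicylate as interpretation.
3. **Section 16.6.4, baseline:** show the same session's pre-dose level and the change from it. Change alone is not enough, because subtracting a fixed pre-dose value over-corrects when an earlier exposure is already declining.
4. **Section 16.6.4, affected sessions:** flag and list wintergreen sessions with recorded salicylate-containing medication before or during the session, or with a pre-dose level above a limit set before the data are seen, for example the assay LLOQ or a small preset fraction of Cmax.
5. **Section 16.6.4, summaries:** give the main summary without the flagged sessions and a second one with all sessions.

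The cost is protocol and analysis-plan wording. Pre-dose samples and concomitant medication are already collected, so no extra sampling is needed. The downside is that a few sessions may drop from the main descriptive summary, and more will drop the lower the pre-dose limit is set; the second summary shows what that changes.

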10.4.2 Collection of used pouches

Used pouches will be collected after 60 minutes (+/- 1 minute) of use for the determination of residual nicotine in the Investigational Products.

All the collected pouches will be frozen immediately at -20°C. Pouches for extraction of nicotine will be analysed by Swedish Match. Pouches from all evaluable subjects will be analysed.

10.5 Adverse events

The Principal Investigator is responsible for ensuring that all medical staff involved in the study is familiar with the content of this section and the content of the CTC standard operating procedures (SOPs) regarding emergencies.

10.5.1 Definition of adverse event

An AE is any untoward medical occurrence in a clinical study subject administered a pharmaceutical product and which does not necessarily have a causal relationship with this treatment. An AE can therefore be any unfavourable and unintended sign (including clinically significant abnormal values from relevant tests, such as clinical safety laboratory tests, vital signs), symptom, or disease temporally associated with the use of an IP, regardless of whether it is considered related to the IP.

A treatment emergent AE (TEAE) is any AE not present prior to the initiation of IP administration or any event already present that worsens in either intensity or frequency following exposure to the IP.

Only TEAEs are collected in this study (*i.e.* events occurring between screening and the first IP administration are regarded as *baseline symptoms* and should not be recorded in the AE log in the eCRF)

10.5.2 Definition of serious adverse event

An SAE is any AE that:

- results in death
- is life-threatening (this refers to an event in which the subject was at risk of death at the time of the event; it does not refer to an event that hypothetically might have caused death had it been more severe)
- requires inpatient hospitalisation or prolongation of existing hospitalisation
- results in persistent or significant disability/incapacity
- is a congenital anomaly/birth defect
- is medically important (this refers to an event that may not be immediately lifethreatening or result in death or hospitalisation, but may jeopardise the subject or may require intervention to prevent any of the SAEs defined above)

Examples of medically important events are intensive treatment in an emergency room for allergic bronchospasm or blood dyscrasias, convulsions that do not result in hospitalisation, development of drug dependency, and drug abuse.

Planned hospitalisations or surgical interventions for a condition that existed before the subject/patient signed the ICF and that did not change in intensity are not SAEs.

If there is any doubt as to whether an AE meets the definition of an SAE, a conservative viewpoint must be taken, and the AE must be reported as an SAE.

10.5.3 Time period and frequency for collecting adverse events

All AEs (including SAEs) will be collected from the start of intervention until the follow-up visit.

Any AE with start date on the day of first IMP administration must be recorded with start time.

At the Follow-up Visit, information on new AEs or SAEs, if any, and stop dates for AEs recorded and on-going during the dosing period must be recorded.

Medical occurrences that begin before the start of study treatment but after obtaining informed consent will be recorded in the Medical History Log of the eCRF, not in the AE Log.

Investigators are not obligated to actively seek AE or SAE after conclusion of the study participation. However, if the investigator learns of any SAE, including a death, at any time after a participant has been discharged from the study, and he/she considers the event to be reasonably related to the study intervention or study participation, the investigator must promptly notify the sponsor.

10.5.4 Assessment of severity/intensity

The grading of the severity/intensity of AEs will follow the CTCAE v4.03 ⁴. Grade refers to the severity of the AE. The CTCAE displays Grades 1 through 5 with unique clinical descriptions of severity for each AE based on this general guideline.

The Investigator must assess the *severity/intensity* of an AE using the following definitions, and record it on the *Adverse Event Form* in the CRF:

Grade 1	Mild; asymptomatic or mild symptoms; clinical or diagnostic
	observations only; intervention not indicated.

- Grade 2 Moderate; minimal, local or non-invasive intervention indicated; limiting age-appropriate instrumental activities of daily living (ADL)*.
- Grade 3 Severe or medically significant but not immediately life-threatening; hospitalization or prolongation of hospitalization indicated; disabling; limiting self- care ADL**.
- Grade 4 Life-threatening consequences; urgent intervention indicated.
- Grade 5 Death related to AE.

10.5.4.1 Assessment of causal relationship

The Investigator must assess the causal relationship between an AE and the IP using the definitions below and record it the Adverse Event Log of the eCRF:

- *Probable* the AE has a strong temporal relationship to the IP or recurs on rechallenge, and another aetiology is unlikely or significantly less likely
- *Possible* the AE has a suggestive temporal relationship to the IP, and an alternative aetiology is equally or less likely
- *Unlikely* the AE has no temporal relationship to the IP or is due to underlying/concurrent illness or effect of another drug (that is, there is no

^{*}Instrumental ADL refer to preparing meals, shopping for groceries or clothes, using the telephone, managing money, etc.

^{**}Self- care ADL refer to bathing, dressing and undressing, feeding self, using the toilet, taking medications, and not bedridden.

causal relationship between the IMP and the AE).

An AE is considered causally related to the use of the IP when the causality assessment is *probable* or *possible*.

10.5.4.2 Assessment of outcome

The Investigator must assess the outcome of an AE using the definitions below and record it on the Adverse Event Log of the eCRF:

- Recovered the subject has recovered completely, and no symptoms remain.
- *Recovering* the subject's condition is improving, but symptoms still remain.
- Recovered with sequelae the subject has recovered, but some symptoms remain (for example, the subject had a stroke and is functioning normally, but has some motor impairment).
- *Not recovered* the subject's condition has not improved and the symptoms are unchanged (for example, an atrial fibrillation has become chronic).
- Death

10.5.5 Collecting adverse events

AEs identified using any of the following methods will be recorded:

- AEs spontaneously reported by the subject
- AEs observed by the Investigator or medical personnel
- AEs elicited based on non-leading questions from the Investigator or medical personnel

10.5.6 Recording adverse events

AEs must be recorded in the AE Log of the eCRF. The investigator must provide information on the AE, preferably with a diagnosis or at least with signs and symptoms; start and stop dates, start and stop time; intensity; causal relationship to IP; action taken, and outcome.

If the AE is serious, this must be indicated in the eCRF.

AEs, including out-of-range clinically significant clinical safety laboratory values, must be recorded individually, except when considered manifestations of the same medical condition or disease state; in such cases, they must be recorded under a single diagnosis.

If the severity/intensity of an AE increases a new AE Form must be completed in the eCRF.

10.5.7 Reporting of serious adverse events

SAE reporting should be performed by the investigator within 24 hours of awareness via the eCRF or by e-mailing a copy of a paper SAE form. All available information regarding the SAE should be entered in the AE Log for the specific subject. By saving the event as "serious" in the eCRF, an e-mail alert is sent to predefined recipients to highlight that an SAE has been registered.

The SAE report is reviewed by a designated person at CTC's Pharmacovigilance (CTC PV) to ensure that the report is valid and correct. For fatal or life-threatening SAEs where important CONFIDENTIAL 33 (50)

[figure not shown]
or relevant information is missing, immediate follow-up is undertaken and queries to the site are raised. Investigators or other site personnel should inform CTC PV of any follow-up information on a previously reported SAE immediately but no later than the end of the next business day of when he or she becomes aware of it.

If the SAE report in eCRF is updated, a new e-mail alert is sent to the predefined recipients.

The appointed Medical Monitor will provide his/her causality assessment and make an expectedness assessment once the report is judged to be complete.

If any additional documentation is required (e.g. autopsy report), CTC PV will request this information from the study site.

In case the eCRF cannot be accessed, the SAE should be reported by manually completing the paper SAE Form, provided in the Investigator Site File. The completed, signed and dated paper SAE Form should, within 24 hours, be scanned and e-mailed to:

The study site should notify the site Monitor via phone or e-mail about the submission of the SAE report. As soon as the site personnel have access to the eCRF, the SAE should be reported electronically as well.

The Sponsor or delegate will assume responsibility for reporting SAEs to IECs in accordance with local regulations.

